##### **4.3.1. Inclusion Criteria**

Refer the most recent version of the protocol for a list of the inclusion criteria.

##### **4.3.2. Exclusion Criteria**

Refer the most recent version of the protocol for a list of the exclusion criteria. .

#### 4.3.3. Withdrawal from the Study or Discontinuation of the Study Product

Subjects may voluntarily withdraw their consent for study participation at any time without penalty or loss of benefits to which they are otherwise entitled. An investigator may also withdraw a subject from receiving the study product for any reason. Follow-up safety evaluations will be conducted if the subject agrees. If a subject withdraws or is withdrawn prior to completion of the study, the reason for this decision must be recorded in the case report forms (CRFs). The reasons, might include, but are not limited to the following:

- Subject no longer meets eligibility criteria
- Subject meets individual halting criteria (refer to the protocol, Section 8.6.2)
- Subject becomes noncompliant
- Medical disease or condition, or new clinical finding(s) for which continued participation, in the opinion of the investigator, might compromise the safety of the subject, interfere with the subject's successful completion of this study, or interfere with the evaluation of responses
- Subject lost to follow-up
- Determined by the investigator's discretion to require additional therapy not indicated in the protocol to ensure subject's health and well-being (or treatment failure, if applicable)

The investigator should be explicit regarding study follow-up (e.g., safety follow-up) that might be carried out despite the fact that the subject will not receive further study product. If the subject consents, every attempt will be made to follow all AEs through the study defined follow-up period, and all SAEs through resolution. The procedures that collect safety data for the purposes of research must be inclusive in the original informed consent or the investigator may seek subsequent informed consent using an Institutional Review Board (IRB) -approved consent form with the revised procedures.

The investigator will inform the subject that already collected data will be retained and analyzed even if the subject withdraws from this study.

#### 4.3.4. Subject Replacement

Subjects who withdraw, are withdrawn from this study, or are lost to follow-up after signing the Informed Consent Form (ICF) and administration of the study product, will not be replaced. Subjects who withdraw, are withdrawn from this study, or are lost to follow-up after signing the ICF, but prior to administration of study product, may be replaced.

#### 4.3.5. Study Termination

If the study is prematurely terminated by the sponsor, any regulatory authority, or the investigator for any reason, the investigator will promptly inform the study subjects and assure appropriate therapy or follow-up for the subjects, as necessary. The investigator will provide a detailed written explanation of the termination to the IRB.

### 4.4. Treatments

#### 4.4.1. Treatments Administered

Subjects will receive either a  $4 \times 10^7$  PFU,  $4 \times 10^8$  PFU, or  $4 \times 10^9$  PFU dose of IV bacteriophage or placebo according to study stage as described in [Figure 1](#).

Bacteriophage should be thawed at room temperature and diluted in normal saline to a final administration volume of 25 mL. The final dilution will be administered as a 30 ( $\pm$  15-35 minutes) minute IV infusion. Placebo will be normal saline at a final volume of 25 mL and administered as a 30 ( $\pm$  15-35 minutes) minute IV infusion. A saline flush will occur after administration of study product or placebo. Collection times for samples will be based on the completion time of the IV flush.

#### 4.4.2. Identity of Investigational Product(s)

##### Bacteriophage

The bacteriophage was packaged in two mL vials. Each vial will contain 1 mL of a single bacteriophage at a concentration of  $1 \times 10^9$  to  $1 \times 10^{11}$  PFU/mL suspended in PlasmaLyte A and 20% (v/v) of glycerol. Bacteriophage is a clear to slightly turbid suspension, essentially free of foreign particulates. The bacteriophage was labeled according to manufacturer specifications and regulatory requirements and include the statement “Caution: New Drug – Limited by Federal Law to Investigational Use.” Additional label contents are detailed in the protocol-specific Manual of Procedures (MOP).

The 4-component bacteriophage mixture will include a 1:1:1:1 combination of four individual bacteriophage (refer to the protocol, Table 2) and will contain a total of  $4 \times 10^7$  PFU,  $4 \times 10^8$  PFU, or  $4 \times 10^9$  PFU, depending on the target dose. The final bacteriophage combination to be administered to each subject will be diluted to the target dose with normal saline. Dosing will be based on the actual product potency, according to instructions that will be provided in the MOP, which will be updated as necessary, based on the most recent potency results.

##### Placebo (Normal Saline, 0.9% Sodium Chloride, US Pharmacopeia [USP])

For the placebo, 0.9% Sodium Chloride Injection, USP, is a sterile, nonpyrogenic, isotonic solution of sodium chloride and water for injection. Each mL contains 9 milligram (mg) of sodium chloride and no preservatives, antimicrobial agents, or added buffer. The solution is clear in appearance with a pH range of 4.5 to 7.0. Normal saline used for the placebo will be supplied in pre-filled infusion bags. Each infusion bag should only be used for one dosing preparation.

The placebo will be labeled according to manufacturer specifications and regulatory requirements and include the statement “Caution: New Drug – Limited by Federal Law to Investigational Use.” Additional label contents are detailed in the protocol-specific MOP.

#### 4.4.3. Method of Assigning Subjects to Treatment Groups (Randomization)

The randomization scheme will be generated and maintained by The Emmes Company, LLC (Emmes). Subjects will be randomized using the Emmes Interactive Web Response System (IWRS).

In Stage 1, two sentinel subjects will each be sequentially assigned to one of three IV bacteriophage doses:  $4 \times 10^7$  PFU,  $4 \times 10^8$  PFU, or  $4 \times 10^9$  PFU. Randomization for Stage 2a and Stage 2b will be performed using a permuted block design, where each site will receive a treatment table accounting for all enrolled study subjects. In Stage 2a, 32 subjects will be randomly assigned to receive one of three IV bacteriophage doses or placebo in a ratio of 1:1:1:1. In Stage 2b, 24-34 subjects will be assigned to either the selected IV bacteriophage dose, selected from the interim analysis results, or placebo in a ratio of 1:1.

#### **4.4.4. Selection of Doses in the Study**

The minimum and maximum doses that are being investigated in this study were informed by previous case reports, case series, and clinical trials, which generally used IV doses ranging from approximately  $10^7$  PFU to  $10^{10}$  PFU (refer to the protocol, Table 1). A single dose is being administered in order to evaluate the safety of the 4-component bacteriophage product prior to moving to a multi-dose regimen.

#### **4.4.5. Selection and Timing of Dose for Each Subject**

Subjects will receive a single 30 ( $\pm$  15-35 minutes) minute IV infusion of bacteriophage or placebo. Sentinel subjects in Stage 1 will be monitored for SAEs for 96 hours after dosing. After Stage 1 enrollment and the 96-hour monitoring period are complete, eligible subjects will be enrolled into Stage 2a and Stage 2b to receive a single IV dose of a 4-component bacteriophage or placebo. The interim analysis will use data from Stage 2a to identify the bacteriophage dose and the sample size that will be used for Stage 2b. For more information regarding selection of dose amounts, refer to Section 4.4.4.

#### **4.4.6. Blinding**

Stage 1 of the study will not be blinded.

A double-blind/masking technique will be used in Stage 2 of the study. The three IV bacteriophage doses and placebo will be packaged identically so that treatment blind/masking is maintained. The subject and the investigator or delegate(s) who are involved in the treatment or clinical evaluation of the subjects will be unaware of the treatment group assignments. To maintain the overall quality and legitimacy of the clinical trial, randomization code breaks should occur only in exceptional circumstances when knowledge of the actual treatment is absolutely essential for further management of the subject. Investigators are encouraged to discuss with study team if he/she believes that unblinding is necessary. Information on laboratory blinding procedures is available in the MOP.

Emergency unblinding of treatment assignment for a subject may be necessary due to a medical emergency or other significant medical events. Procedures for emergency unblinding are detailed in the MOP. The treatment assignment code list will be kept in a secure place at all times at the responsibility of the Statistical and Data Coordinating Center (SDCC), at Emmes.

#### **4.4.7. Prior and Concomitant Therapy**

Any systemic medication taken by the subject, other than study drugs, is considered a concomitant medication. All concomitant medications from Screening (Visit 1) through Day  $30 \pm 7$  (Visit 7) must be recorded in the subject's medical record and on the electronic case report forms (eCRFs).

If a subject is prescribed antibiotic therapy with activity against *P. aeruginosa* after receipt of the study product, the subject will continue in the study and be included in an intent-to-treat (ITT) analysis. Receipt of antibiotic therapy with activity against *P. aeruginosa* will be documented as a concomitant medication and the underlying condition for which the antibiotics were taken will be reported as an AE.

#### **4.4.8. Treatment Compliance**

Subjects will be directly observed while receiving a single dose of study product or placebo by a member of the study team who is licensed to administer the study product or placebo. Administration data will be recorded in the source and entered into the eCRF.

## 4.5. Primary Endpoint Variables

The three primary objectives are as follows: (1) the safety of a single dose of IV bacteriophage therapy in clinically stable CF subjects with *P. aeruginosa* in expectorated sputum, (2) the microbiological activity of a single dose of IV bacteriophage therapy in clinically stable CF subjects with *P. aeruginosa* in expectorated sputum, and (3) the benefit to risk profile of a single dose of IV bacteriophage therapy in clinically stable CF subjects with *P. aeruginosa* in expectorated sputum.

The safety endpoint will be measured by the number of Grade 2 or higher treatment-emergent AEs through Day  $30 \pm 7$ . Safety will also be assessed through the incidence of treatment-emergent adverse events (TEAEs), on-therapy SAEs, and AEs leading to premature discontinuation. Adverse events will be graded according to the Common Terminology Criteria for Adverse Events (CTCAE) Version 5.0, November 2017 ([https://ctep.cancer.gov/protocoldevelopment/electronic\\_applications/ctc.htm#ctc\\_50](https://ctep.cancer.gov/protocoldevelopment/electronic_applications/ctc.htm#ctc_50)). Details about adverse event grading and determination of relationship to study product can be found in the protocol, Section 8.1.1.1.

Clinical laboratory results, including chemistry, hematology, and liver function tests, will also be graded according to the CTCAE scale. Clinical chemistry parameters include serum creatinine, blood urea nitrogen (BUN), glucose, sodium, potassium, chloride, bicarbonate, and calcium. Hematology parameters include complete blood count with red blood cell (RBC) count, hemoglobin, hematocrit, total white blood cell (WBC) count with differential counts, and platelet count. Liver function tests include aspartate aminotransferase (AST), alanine aminotransferase (ALT), alkaline phosphatase, total bilirubin, lactate dehydrogenase, albumin, and total protein. Only AST, ALT, and total bilirubin are collected at Screening. Clinical chemistry, hematology, and liver function tests will be performed at baseline and at follow-up visits occurring on Days 2, 5, 8, 12 (Stage 1 only), and 30. Refer to Section 3.3.2 for the definition of baseline.

The microbiological activity endpoint will be measured based on the change in  $\log_{10}$  *P. aeruginosa* colony counts after administration of IV bacteriophages/placebo. Sputum collection for measuring colony counts will occur at baseline and at follow-up visits occurring on Days 2, 5, 8, and 30.

Finally, DOOR will be used to describe the benefit to risk profile based on the greatest reduction in DOOR category by the Day 8 + 3 follow-up visit. DOOR is a composite endpoint which includes whether or not a subject experienced an SAE (related to study product) and what category their reduction in *P. aeruginosa* colony counts falls into;  $>2 \log_{10}$  reduction in CFU/mL, 1-2  $\log_{10}$  reduction in CFU/mL, or  $<1 \log_{10}$  reduction in CFU/mL.

## 4.6. Exploratory Endpoint Variables

There will be four exploratory objectives: (1) characterize the serum and sputum PK profiles of a single dose of IV bacteriophage therapy in clinically stable CF subjects with *P. aeruginosa* in expectorated sputum, (2) change in lung function from the administration of a single dose of IV bacteriophage therapy through Day  $30 \pm 7$ , (3) characterize geographically diverse *P. aeruginosa* isolates susceptibility to bacteriophages, and (4) describe subjects' QoL before and after receiving bacteriophages. The SAP for the first exploratory objective, related to serum and sputum PK, will be provided in a separate document.

Change in lung function will be measured using FEV1. Spirometry will be performed at screening, baseline, and at follow-up visits occurring on Days 2, 5, 12, and 30.

Phage susceptibility testing (PST) will occur using a plaque assay and the liquid assay. These assays describe the proportion of *P. aeruginosa* isolates that are susceptible to each phage and to the phage cocktail. Both the plaque assay and liquid assay will be evaluated every time sputum is obtained (see schedule of study

procedures in [Table 1](#)). An isolate will be considered susceptible to phage if both the plaque assay and the liquid assay indicate susceptibility.

The CFQ-R (<https://cfqr-app.netlify.app/#/questionnaire>) is a self-administered QoL questionnaire designed to measure the impact that CF has on overall health, daily life, and perceived well-being and symptoms. The CFQ-R contains 50 items and will be administered at in-person and virtual study visits for Stage 2 subjects. The CFRSD (<https://depts.washington.edu/seaqol/CFRSD-CRISS>) is a subject reported outcome measure that is used to evaluate the effect of treatment on respiratory infection symptom severity in patients with CF and chronic respiratory infection. Quality of Life will be measured using the CFQ-R and the CFRSD. The CFQ-R will be administered at baseline and at the final follow-up visit (Day  $30 \pm 7$ ). The CFRSD will be administered at baseline and at follow-up visits occurring on Day 2, 5, 8, and 30.

## 5. SAMPLE SIZE CONSIDERATIONS

The sample size for Stage 2 (Stage 2a/2b) was determined using DOOR. The sample size was calculated to provide desired precision of the estimate of the DOOR probability in order to describe the benefit to risk profile of a single dose of IV bacteriophage in clinically stable CF subjects with *P. aeruginosa* in expectorated sputum. If the true DOOR probability comparing IV bacteriophage and placebo is 70%, when the total sample size in each arm is 20-25 (combining subjects from Stages 2a and 2b), the two-sided normal approximate 95% confidence interval (CI) for DOOR probability is calculated at 51% and 89%, respectively, with the lower limit larger than 50%.

An interim analysis will be performed when the eight subjects per arm in Stage 2a ( $40\% = 8/20$ ) have completed the follow-up through their last follow-up visit, which will be Day  $30 \pm 7$  if they complete all follow-up visits. Only a single dosage of IV bacteriophage therapy to be used in Stage 2b will be determined during the interim analysis and the planned sample size will be re-evaluated to whether it provides the desired precision of estimates of the DOOR probability for a selected dose and placebo. If necessary, after completion of Stage 2a and per details in Section 6.6, the sample size will be increased up to 17 subjects for each of the two arms in Stage 2b (a total of up to 25 for the placebo arm and up to 25 for the selected bacteriophage dose in Stage 2).

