10.2 Sample Size Considerations

The sample size for Stage 2 (Stage 2a/2b) was determined using the DOOR outcome measure. The sample size was calculated to provide desired precision of the estimate of the DOOR probability in order to describe the benefit to risk profile of a single dose of IV bacteriophage in clinically stable CF subjects with *P. aeruginosa* in expectorated sputum. If the true DOOR probability comparing IV bacteriophage and placebo is 70%, when the total sample size in each arm is 20 (combining subjects from Stages 2a and 2b), the two-sided normal approximate 95% confidence interval for DOOR probability is calculated at 51% and 89%, respectively, with the lower limit larger than 50% (see Section 10.5.5).

An interim analysis will be performed when the 8 subjects per arm in Stage 2a ($40\% = 8/20$) have completed their Day 8 + 3 days Follow-up Visit (Section 10.4.2). Based on the observed data, two of the doses of IV bacteriophage therapy will be dropped from the study at the interim analysis, and the planned sample size will be re-evaluated as to whether it provides the desired precision of estimates of the DOOR probability for a selected dose and placebo. If necessary, after completion of Stage 2a and per details in Section 10.4.2, the sample size will be increased up to 17 subjects for each of the two arms in Stage 2b (a total of up to 25 for the placebo arm and up to 25 for the selected bacteriophage dose in Stage 2).

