10.4.2 Interim Microbiological Activity Review

An interim analysis will be performed to select the IV bacteriophage dose with the most favorable benefit to risk profile compared to placebo for further evaluation in Stage 2b, and to exclude proceeding with bacteriophage doses that do not reduce pseudomonal colony counts or are associated with safety issues, when all subjects in Stage 2a have completed their Day 8 + 3 days Follow-up Visit or last study visit if early withdrawal.

Continuous variables will be summarized by number of subjects, mean, standard deviation (SD), median, quartiles (1st and 3rd quartiles), minimum, and maximum values. Categorical variables will be summarized by number and percentage of subjects. The interim analysis will consist of a quantitative evaluation of potential effect sizes and associated precision using a predicted intervals and predicted interval plots approach.²⁹ Briefly, predicted intervals for DOOR probability will be calculated under a range of assumptions including: (1) the trends in outcomes

observed at interim analysis will continue to end of study, (2) both DOOR distributions are identical, and (3) best and worst case scenarios for remaining outcomes. By relying on prediction intervals, no statistical hypothesis testing is required and no power is lost at interim analysis. In addition, as supplementary information, (predictive) conditional power will be calculated to quantify the probability of rejecting the null hypothesis, i.e., DOOR probability $\leq 50\%$, at the final analysis under a range of assumptions.

Similar to DOOR, changes in $\log_{10} P. aeruginosa$ CFU/mL (total and each morphology) in sputum cultures from administration of IV bacteriophages through Day 8 + 3 days, will be evaluated, using predicted interval plots to assess the precision for measuring differences in \log_{10} CFU/mL count.

The planned sample size (20 subjects per Stage 2b arm) will be reevaluated after completion of Stage 2a. If necessary, the sample size will be increased up to 25 subjects for the two arms in Stage 2b (up to 25 subjects for the placebo arm and up to 25 subjects for the selected bacteriophage dose) to provide the desired precision of estimates.

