## 6.6. Interim Analyses and Data Monitoring

An interim analysis will be performed when all randomized subjects for Stage 2a have completed follow-up, through Day  $30 \pm 7$ , or the last study visit for those who withdrew early.

The purpose of the interim analysis will be to select one IV bacteriophage dose with the most favorable benefit to risk profile compared to placebo for further evaluation in Stage 2b. The interim analysis will also serve to exclude proceeding with bacteriophage doses that are associated with safety issues, do not reduce pseudomonal colony counts, or have low conditional power. An independent statistician at the SDCC will report to the Phage Advisory Group. The Phage Advisory Group will make a recommendation to the DMID on the selected dose to be considered for Stage 2b. This will only be a recommendation. Ultimately, DMID will review the recommendation (as well as the DSMB recommendation based on independent review of safety and microbiological activity data) and make the final decision on how to proceed regarding Stage 2b.

The interim analysis will consist of a quantitative evaluation of potential effect sizes and associated precision using predicted intervals and predicted interval plots (PIPs) approach. Predicted intervals for DOOR probability will be calculated under the range of assumptions outlined in Section 8.3.

By relying on prediction intervals, no statistical hypothesis testing is required, and no power is lost at interim analysis [1]. In addition, as supplementary information, (predictive) conditional power will be calculated to quantify the probability of rejecting the null hypothesis at the final analysis under a range of assumptions, which are listed in Section 8.3.

Similar to DOOR, changes in  $\log_{10}$  *P. aeruginosa* colony counts (total and each morphology) in sputum cultures from administration of IV bacteriophages through Day  $8 + 3$ , will be evaluated using PIPs to assess the precision for measuring differences in  $\log_{10}$  CFU/mL count.

The planned sample size (20 subjects per Stage 2b arm) will be reevaluated after completion of Stage 2a. If necessary, the sample size will be increased up to 25 subjects for the two arms in Stage 2b (up to 25 subjects for the placebo arm and up to 25 subjects for the selected bacteriophage dose) to provide the desired precision of estimates.

Details of the interim analysis are provided in Section 8.3.

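### SAP Section 5 gives one interval (51% to 89%) for 20-25 subjects per arm although it belongs to 20 per arm only, and Protocol 10.4.2 and SAP 6.6 label combined Stage 2a and 2b totals as Stage 2b arm sizes

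*SAP*

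**What the plan says.** **Precision.** SAP Section 5 assumes a true DOOR probability of 70% and sets this condition on size: "when the total sample size in each arm is 20-25 (combining subjects from Stages 2a and 2b"). For that whole range it reports a single result: "the two-sided normal approximate 95% confidence interval (CI) for DOOR probability is calculated at 51% and 89%, respectively". It adds that the lower limit lies above 50%. Protocol 10.2 reports the same limits, but for one size: "when the total sample size in each arm is 20 (combining subjects from Stages 2a and 2b"). Neither document states the variance behind the interval.

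**Planned size.** Protocol 10.2 allows an increase after Stage 2a: "per details in Section 10.4.2, the sample size will be increased up to 17 subjects". The figure of 17 applies to each Stage 2b arm and makes up to 25 per arm over Stage 2. SAP Section 5 says the same: "per details in Section 6.6, the sample size will be increased up to 17 subjects for each of the two arms in Stage 2b". The sections they point to use other words. Protocol 10.4.2 first describes the plan: "The planned sample size (20 subjects per Stage 2b arm) will be reevaluated after completion of Stage 2a". It then describes the possible increase: "If necessary, the sample size will be increased up to 25 subjects for the two arms in Stage 2b". SAP 6.6 repeats both sentences and ends: "Details of the interim analysis are provided in Section 8.3". SAP 8.3 describes 20 per group as the combined Stage 2a and 2b total, which may rise to 25.

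**The concern.** The width of a confidence interval depends on the sample size, so one interval cannot describe both 20 and 25 per arm. This matters because precision of the DOOR probability is the only rationale given for the sample size, and the re-evaluation after Stage 2a asks whether precision is adequate. Showing the same interval at both sizes implies that five more subjects per arm gain nothing.

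The labelling matters for a related reason. A reader who follows the cross-reference for the detail of the increase arrives at two sections that attach the combined totals to Stage 2b alone.

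**Working it through.** **Inputs.** DOOR probability p = 0.70, two-sided 95%, normal quantile z = 1.960, and n per arm of 20 (Protocol 10.2) or 20-25 (SAP 5). The stated half-width is 0.89 - 0.70 = 0.19. The variance is not given, so it is varied here.

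**The plan's own figure at n = 20.** With the null Wilcoxon-Mann-Whitney variance and no ties, SE = sqrt((2n+1)/(12n²)) = sqrt(41/4800) = 0.0924. The half-width is 0.181 and the interval 51.9% to 88.1%, within one point of the stated limits but not equal to them. Two variants do round to 51%-89% at 20:
- the same SE with a t quantile on 38 degrees of freedom (51.3% to 88.7%), although the plan names a normal approximation;
- the null variance with (n-1)² in the denominator (50.9% to 89.1%).

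**The same question at n = 25, with 25 complete observations per arm.**

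| Basis | Half-width at 25 | Interval at 25 |
|---|---|---|
| Largest possible variance, p(1-p)/n: 1.96 × sqrt(0.21/25) | 0.180 | 52.0% to 88.0% |
| Stated half-width rescaled: 0.19 × sqrt(20/25) | 0.170 | 53.0% to 87.0% |
| (n-1)² variant | 0.168 | 53.2% to 86.8% |
| t-quantile variant | 0.166 | 53.4% to 86.6% |
| Null variance, no ties: 1.96 × sqrt(51/7500) | 0.162 | 53.8% to 86.2% |

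None of these rounds to 51%-89%. The excess at each end is 0.19 - 0.180 = 0.010, 0.19 - 0.170 = 0.020 and 0.19 - 0.162 = 0.028 on the three main bases. The rescaled row isolates the effect of n, at about 2 points. In the null-variance row, 0.19 - 0.181 = 0.009 of the gap is already there at n = 20 and reflects the choice of variance.

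**The check in reverse.** For 51%-89% to be right at 25, the half-width there must be at least 0.185, the smallest value that rounds to 0.19. At 20 it would then be about 0.185 × sqrt(25/20) = 0.207, and the lower limit about 49.3%. That contradicts Protocol 10.2 and the statement in SAP 5 that the lower limit exceeds 50%.

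**Arm sizes.** Stage 1 has 6 subjects and Stage 2a has 32, or 8 per arm.
- As planned: 8 + 12 = 20 and 8 + 17 = 25 per arm. The trial totals are 6 + 32 + 24 = 62 and 6 + 32 + 34 = 72.
- With 20 or 25 taken literally as Stage 2b arm sizes: 8 + 20 = 28 and 8 + 25 = 33 per arm. The trial totals would be 6 + 32 + 40 = 78 and 6 + 32 + 50 = 88.

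The first reading agrees with Figure 1 of the Protocol (about 12-17 per Stage 2b arm, about 20-25 combined), the 24-34 Stage 2b subjects in SAP 2, 4.1 and 4.4.3, the maximum of 72 in Protocol 3.1 and SAP 4.1, and the interim fraction of 40% = 8/20 in Protocol 10.2 and SAP 5. The literal reading would give 8/28 = 29% or 8/33 = 24%.

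**The case against.** **The figure of 54%-86% at 25 is not established.** This stands. It comes from a null variance without ties, which the plan does not name and which gives 52%-88%, not 51%-89%, at 20. DOOR has four ranks, and SAP 8.1.3 corrects for ties. As an assumed illustration, take ranks 1 to 4 as 10/20/70/0% on placebo and 35/32/33/0% on phage, a DOOR probability of about 0.70. The tie-corrected null half-widths are then about 0.165 at 20 and 0.148 at 25, narrower again. A reader might infer that 54%-86% is the correct entry, or that the whole 3-point gap comes from n. The documents support neither. They support only that 51%-89% is too wide at 25.

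**Missing data could widen the interval.** With 23 contributing per arm, the largest-variance bound is 51.3% to 88.7%, which rounds to the stated limits. But SAP 5 speaks of total sample size at both ends of its range, and on that same basis 20 per arm gives 49.9% to 90.1%, with a lower limit below 50%. This does not rescue the sentence.

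**The labelling is loose rather than contradictory in intent.** Much of this stands. Both sections go on to give up to 25 for placebo and up to 25 for the selected dose, SAP 6.1 defines both groups over Stages 2a and 2b, and SAP 6.6 defers to SAP 8.3, which is right. A reader might infer a planned enrolment of 78 or 88. The maximum of 72 and the 24-34 in Stage 2b rule that out.

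**Nothing depends on it.** Also largely true. The final interval uses the Halperin method of SAP 8.1.3, not the planning figure.

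**Conclusion.** Both defects are real and minor. The interval in SAP 5 is the Protocol's figure for 20 per arm applied to a range that runs to 25. At 25 it is about 1 to 3 points too wide at each end across the three main bases, with about 2 points attributable to n. This assumes a DOOR probability of 70%, a normal quantile and 25 complete observations per arm. The exact limits at 25 cannot be given until the sponsor names the variance.

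The error is conservative. A reader might infer that the sample-size rationale fails, but the lower limit stays above 50% at 25 on every basis computed, including the largest possible variance.

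The Stage 2b labels in Protocol 10.4.2 and SAP 6.6 are wrong as worded, but the intended meaning is clear from the rest of the plan.

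**What to change.** - **SAP 5:** name the planning variance, including how ties are handled, and state one interval for 20 per arm and one for 25 on that basis. Keep 51%-89% for 20 only, and only if the named variance gives it.
- **Protocol 10.4.2 and SAP 6.6:** replace the wording with: *20 subjects per arm in total over Stages 2a and 2b, increased if necessary to up to 25 per arm in total.* This matches SAP 8.3.

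The cost is a few sentences in three sections. No subjects are added, and neither enrolment nor any analysis changes.
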